7.4.3. Outcome Variables

Primary and secondary outcomes specific to each objective are outlined in Table 5 below. Note, all outcomes described below are collected from the index date in both study Cohorts.

Table 5: Outcome Variables

Variable	Captured in DHR	DHR data field name(s)	Operational definition and calculation of outcome measures	Timepoints for data collection
Bleeding Events				
Treated ABR	Yes (calculated)	
 Therapy scheme Occasion Date of bleed Therapy start End of therapy 	
 Number of treated bleeding events per year Calculate ABR using number of treated bleed events within the relevant time period (≥ 1 year of follow-up, ≥ 2 years of follow-up, ≥ 3 years of follow-up, all available follow-up) 
 A bleeding event is captured if occasion for therapy is spontaneous bleeding/hemorrhage (regardless of severity) Bleeds will be identified as treated bleeds if they meet one of the following criteria: 
 If bleed date is within 3 calendar days of treatment date where occasion for treatment is one of the hemorrhage values OR therapy scheme is "on demand" If multiple bleeds with different localization occur on the same calendar day of the last bleed before treatment for bleed, the subsequent treatment within 3 calendar days is considered to pair with each of these bleeds; Each of these bleeds that is within 3 calendar days of the subsequent treatment is therefore considered to be a treated bleed Two bleeds of the same localization are considered to be one bleed if the second occurs within 3 calendar days from the date of the last treatment for the first bleed; The last treatment is defined as the last treatment before a new bleed occurs, either in the same or in a different location regardless of whether the second bleed is followed by a treatment 	
 ≥ 1 year ≥ 2 years ≥ 3 years All available follow-up

Variable	Captured in DHR	DHR data field name(s)	Operational definition and calculation of outcome measures	Timepoints for data collection
			
 Calculate annualized metric of the number of bleeding events by dividing the number of bleeds by the number of days in the relevant time period, multiplied by 365.25 	
Major ABR	Yes (calculated)	
 Occasion Severity Date of bleed 	
 Number of major bleeding events per year Calculate ABR using number of bleed events within the relevant time period (≥ 1 year of follow-up, ≥ 2 years of follow-up, ≥ 3 years of follow-up, all available follow-up) Major bleeds are defined as treated bleeds (see definition above) with severity recorded as “severe” or “life-threatening” (irrespective of location) 
 Note: a bleeding event is captured if occasion for therapy is spontaneous bleeding/hemorrhage (regardless of severity) Definition of “severe” and “life-threatening” severity will be consistent with existing practices in the DHR¹ Calculate annualized metric of the number of bleeding events by dividing the number of bleeds by the number of days in the relevant time period, multiplied by 365.25 	
 ≥ 1 year ≥ 2 years ≥ 3 years All available follow-up
Life-threatening ABR	Yes (calculated)	
 Occasion Severity Date of bleed 	
 Number of life-threatening bleeding events per year Calculate ABR using number of bleed events within the relevant time period (≥ 1 year of follow-up, ≥ 2 years of follow-up, ≥ 3 years of follow-up, all available follow-up) Life-threatening bleeds are defined as treated bleeds (see definition above) with severity recorded as “life-threatening” (irrespective of location) 
 Note: a bleeding event is captured if occasion for therapy is spontaneous bleeding/hemorrhage (regardless of severity) Life-threatening bleeds will be a subset of treated bleeds and major bleeds Definition of “life-threatening” severity will be consistent with existing practices in the DHR¹ Calculate annualized metric of the number of bleeding events by dividing the number of bleeds by the number of days in the relevant time period, multiplied by 365.25 	
 ≥ 1 year ≥ 2 years ≥ 3 years All available follow-up

Variable	Captured in DHR	DHR data field name(s)	Operational definition and calculation of outcome measures	Timepoints for data collection
Joint ABR	Yes (calculated)	
 Occasion Localization Date of bleed 	
 Number of joint bleeding events per year Calculate ABR using number of bleed events within the relevant time period (≥ 1 year of follow-up, ≥ 2 years of follow-up, ≥ 3 years of follow-up, all available follow-up) Joint bleeds are defined as treated bleeds (see definition above) and based on localization of bleed 
 Note: a bleeding event is captured if occasion for therapy is spontaneous bleeding/hemorrhage (regardless of severity) Calculate annualized metric of the number of bleeding events by dividing the number of bleeds by the number of days in the relevant time period, multiplied by 365.25 	
 ≥ 1 year ≥ 2 years ≥ 3 years All available follow-up
% Zero treated bleeds	Yes (calculated)	
 Therapy scheme Occasion Start of reporting period End of reporting period 	
 % Of participants with zero treated bleeds calculated based on treated bleeding No bleeding events captured within the reporting period start and stop dates The number of participants within the Cohort with zero treated bleeds is divided by the total number of participants in the Cohort See definition for treated bleed above to be used to derive this variable 	
 ≥ 1 year ≥ 2 years ≥ 3 years All available follow-up
% Zero major bleeds	Yes (calculated)	
 Occasion Severity Start of reporting period End of reporting period 	
 % Of participants with zero major bleeds calculated based on major bleeding No bleeding events captured within the reporting period start and stop dates The number of participants within the Cohort with zero major bleeds is divided by the total number of participants in the Cohort See definition for major bleed above to be used to derive this variable 	
 ≥ 1 year ≥ 2 years ≥ 3 years All available follow-up
% Zero life-threatening bleeds	Yes (calculated)	
 Occasion Severity Start of reporting period End of reporting period 	
 % Of participants with zero life-threatening bleeds calculated based on life-threatening bleeding No bleeding events captured within the reporting period start and stop dates The number of participants in the Cohort with zero life-threatening bleeds is divided by the total number of participants in the Cohort See definition for life-threatening bleed above to be used to derive this variable 	
 ≥ 1 year ≥ 2 years ≥ 3 years All available follow-up

Variable	Captured in DHR	DHR data field name(s)	Operational definition and calculation of outcome measures	Timepoints for data collection
% Zero joint bleeds	Yes (calculated)	
 Occasion Localization Start of reporting period End of reporting period 	
 % Of participants with zero joint bleeds calculated based on joint bleeding No bleeding events captured within the reporting period start and stop dates The number of participants in the Cohort with zero joint bleeds is divided by the total number of participants in the Cohort See definition for joint bleed above to be used to derive this variable 	
 ≥1 year ≥2 years ≥3 years All available follow-up
Treatment Outcomes				
Use of any hemostatic treatments	Yes	
 Preparation/medicinal product Start of reporting period End of reporting period 	
 Participants with any hemostatic medication use during the follow-up period 	
 ≥1 year ≥2 years ≥3 years All available follow-up
Prophylactic hemostatic treatments	Yes (calculated)	
 Occasion Preparation/medicinal product Weight Consumption/delivery Treatment date Start of reporting period End of reporting period 	
 Amount of prophylactic hemostatic treatments utilized per participant over time (IU or mg), as well as per participant per kg over time (IU/kg) for FVIII products and mg/kg for emicizumab Each participant's average weight over the reporting period will be used when calculating IU/kg 	
 ≥1 year ≥2 years ≥3 years All available follow-up
On-demand hemostatic treatments	Yes (calculated)	
 Occasion Preparation/medicinal product Weight Consumption/delivery Treatment date Start of reporting period 	
 Amount of on-demand FVIII utilized per participant over time (IU or mg), as well as per participant per kg over time (IU/kg) for FVIII products and mg/kg for emicizumab for a bleeding event (occasion = "suspected bleeding", "spontaneous bleeding", "traumatic bleeding/bleeding", or "intensified on-demand treatment (=short-term prophylaxis)") Amount of on-demand FVIII utilized per participant over time (IU or mg), as well as per participant per kg over time (IU/kg) for FVIII products and mg/kg for emicizumab for short-term prophylaxis (occasion = "intensified on-demand treatment (=short-term prophylaxis)") 	
 ≥1 year ≥2 years ≥3 years All available follow-up

Variable	Captured in DHR	DHR data field name(s)	Operational definition and calculation of outcome measures	Timepoints for data collection
		
 End of reporting period 	
 Each participant's average weight over the reporting period will be used when calculating IU/kg 	
FVIII Infusion/injection rate	Yes (calculated)	
 Preparation/ medicinal product Frequency Start of reporting period End of reporting period 	
 Number of infusions/injections from the index date through the follow-up period Derived based on the therapy usage and frequency of use during individual usage periods recorded in the DHR for any reason and summarized as AIR 	
 ≥1 year ≥2 years ≥3 years All available follow-up
Time to resumption of prophylactic treatment	Yes	
 Did the patient have to return for prophylaxis? Date of return to prophylaxis Date of gene therapy 	
 Roctavian Cohort only Derived based on the recording of whether the patient had to return for prophylaxis and if yes, the time (days) between the date of gene therapy and date of return to prophylaxis 	All available follow-up
Clinical Outcome Assessments				
HJHS	Yes (calculated)	
 Date of the joint score Score used Joint score Score overall movement patten 	
 For each participant, the HJHS domains are expected to be collected at baseline (index date) and annually during the follow-up period The change from baseline will be calculated and a repeated measures model will be used to account for the scores at different time points HJHS are calculated for the left and right elbow, left and right knee, and left and right ankle, as well as a global gait score; Scores will be calculated for each joint and for the global gait score 	All available follow-up
Haemo-QoL-A	Yes		
 For each participant, the Haemo-QoL-A questionnaire are expected to be collected at the baseline and every 6 months during the follow-up period The change from baseline will be calculated and a repeated measures model will be used to account for the administration at different time points Haemo-QoL-A scores are calculated as a total score including all six domains and for each of the six domains separately (physical functioning, role functioning, worry, consequences of bleeding, emotional impact and treatment concerns); Scores will be calculated for the total and each of these six domains 	All available follow-up

Variable	Captured in DHR	DHR data field name(s)	Operational definition and calculation of outcome measures	Timepoints for data collection
BPI-sf	Yes		
 For each participant, the BPI-sf questionnaire is expected to be collected at the baseline and every 6 months during the follow-up period The change from baseline will be calculated and a repeated measures model will be used to account for the administration at different time points BPI-sf measures will be reported for pain intensity (Question 5 of BPI-sf that describes participants' pain on average) and pain interference (average of the seven subitems of Question 9 of BPI-sf) 	All available follow-up
Safety Outcomes				
All cause death	Yes	
 Reason for resignation Cause of death Date of retirement 	
 Any participants with reason for resignation from DHR as "deceased" and cause of death as "hemophilia-related", "non-hemophilia-related", or "unknown" 	All available follow-up
Hemophilia-related death	Yes	
 Reason for resignation Cause of death Date of retirement 	
 If reason for resignation from DHR is "deceased" and cause of death is captured as "hemophilia-related" 	All available follow-up
AEs leading to hospitalization and death	Yes	
 Medically relevant events in this reporting period Relation to hemophilia treatment Serious consequences due to relevant events 	
 Identified if serious consequences due to relevant events = "hospitalization" or "death"² Events will be analyzed both for any reason (regardless of relation to hemophilia treatment) and related to hemophilia treatment 	All available follow-up
Development of FVIII inhibitors	Yes (calculated)	
 Inhibitor tests against FVIII/FIX positive in this reporting period Date of the inhibitor test Titer Test assay used 	
 If inhibitor tests against FVIII/FIX were performed during the reporting period, participants with a positive test will be identified Based on any recording of the DHR variables for inhibitors developed during the reporting period, positive inhibitor tests during the reporting period, or use of ITT (occasion = "ITT") Titer (BU/ml) 0.0-1000.0 	All available follow-up

Variable	Captured in DHR	DHR data field name(s)	Operational definition and calculation of outcome measures	Timepoints for data collection
		
 Occasion 		
Thrombo-embolic events	Yes	
 Other relevant event Relation to hemophilia treatment 	
 Thromboembolic events connected to hemophilia treatment will be identified if other relevant event = “thromboembolic event” and relation to hemophilia treatment = “yes” 	All available follow-up
Malignant neoplasms	Yes	
 Other relevant event Relation to hemophilia treatment 	
 Derived based on recording of medically relevant event of malignant neoplasm in the DHR³ Malignant neoplasms connected to hemophilia treatment will be identified if other relevant event = “neoplasm” and relation to hemophilia treatment = “yes” Occurrence of malignant neoplasm regardless of relationship to treatment will also be described, but not compared Malignancies are expected to be defined consistent with other data collection occurring in the study population, including the World Federation of Hemophilia Gene Therapy Registry^{20, 21} 	All available follow-up
Severe liver disease	Yes	
 Liver disease status Date of liver fibrosis (new diagnosis) Relation to hemophilia treatment 	
 Derived based on recording of liver disease status (liver fibrosis [new diagnosis], liver failure, and liver cirrhosis) 
 Recording during follow-up of “liver fibrosis (new diagnosis)” or “liver failure” will be used to identify events Progression of fibrosis or cirrhosis will be identified based on recording of an increased grade of liver fibrosis/cirrhosis relative to liver disease status at baseline Severe liver disease connected to hemophilia treatment will be identified if relation to hemophilia treatment = “yes” Both events regardless of relationship to hemophilia treatment and specifically related to hemophilia treatment will be analyzed Progression of fibrosis or cirrhosis will be identified based on recording of an increased Child-Turcotte-Pugh classification (e.g., A → B, B → C) of liver disease relative to liver disease status at baseline or the new diagnosis of cirrhosis¹⁷⁻¹⁹ The definition of severe liver disease is consistent with other data collection occurring in the study population, including the international World Federation of Hemophilia Gene Therapy Registry^{20, 22} 	All available follow-up

Variable	Captured in DHR	DHR data field name(s)	Operational definition and calculation of outcome measures	Timepoints for data collection
			
 Definitions of acute liver failure, liver fibrosis and/or progression of liver fibrosis, or cirrhosis will be consistent with MSD Manuals of classification¹⁷⁻¹⁹ 	

Abbreviations: AbD: Anwendungsbegleitende Datenerhebung; ABR: annualized bleeding rate; AE: adverse event; AIR: annualized infusion/injection rate; BPI-sf: Brief Pain Inventory-short form; BU/ml: Bethesda unit/milliliter; DHR: Deutsches Hämophileregister; ED: exposure days; FVIII: coagulation factor VIII; FIX: coagulation factor IX; HJHS: Hemophilia Joint Health Score; IU: international unit; ITT: immune tolerant therapy; kg: kilogram; MCID: minimal clinical important difference; mg: milligram; PRO: patient reported outcome; QoL: quality of life; SoC: standard of care.

Note: Data fields in the DHR are either mandatory to be entered into the registry per DHR practices or will be monitored to ensure completeness of data for analyses, however responses may still be unknown.

1. Definition confirmed by DHR as consistent with PedNet. A bleed is classified as severe if the bleed causes pain, swelling, and/or mobility disability and does not end within 24 hours. A bleed is classified as life threatening if the bleed is severe (causes pain, swelling, and/or mobility disability and does not end within 24 hours) and poses a special risk to the patient.
2. Hospitalization defined as a participant having been admitted to the hospital for inpatient care, either to the inpatient ward or to the emergency room for observation and/or treatment that would not have been appropriate in the physician's office or outpatient setting.
3. Malignant neoplasms have cells that grow uncontrollably and spread locally and/or to distant sites. Malignant tumors are cancerous (i.e., they invade other sites). They spread to distant sites via the bloodstream or the lymphatic system. This spread is called metastasis. Metastasis can occur anywhere in the body.²³

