3.2.2.2. Factor VIII substitution

FVIII concentrates derived from human plasma or manufactured by recombinant technologies in cell culture can be used for hemostatic prophylaxis. The half-life of FVIII in plasma is 10 to 12 hours. Therefore, it is necessary to inject plasma-derived or standard half-life FVIII concentrates at least 3 times per week. Factor VIII drugs with extended half-lives can reduce injection frequency or increase trough levels. Various techniques are used to delay clearance, such as fusion techniques or pegylation (covalent binding of polyethylene glycol (PEG) at particular points on the FVIII molecule). Fusion involves other recombinant proteins, such as the Fc domain of immunoglobulins, which have a substantially longer half-life in the blood and protect against early degradation. The half-life of FVIII is limited by binding to von Willebrand factor. For the dosing frequency to be reduced from 3 times to twice per week while maintaining coagulation factor levels, the half-life needs to be at least 1.3 times that of a standard FVIII drug ([Miesbach 2019](#)).

The list of approved factor VIII products used in Germany for the prophylactic treatment of severe HA can be found on the website of the Paul-Ehrlich-Institute ([Paul Ehrlich Institute 2023b](#)).

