7.4.2. Exposure Variables

Once inclusion and exclusion criteria are applied to the study population, Table 4 will be used to identify index medications for the Roctavian and SoC Cohorts. This table identifies all drug names as well as the frequency and dosage within each treatment group. Dosages are participant dependent, calculated based on the participant's weight (see Table 3 for weight variable details). Note, the index medication will be Roctavian administration for the Roctavian Cohort and the prophylaxis administration closest to and before the study consent for the SoC Cohort.

To account for any potential concerns regarding heterogeneity of SoC treatments, a sensitivity analysis is planned to analyze the SoC treatment types separately, as outlined in Section 7.9.5.

Treatment patterns, switching between SoC treatment classes (SHL, EHL, PD, and emicizumab), and switching between FVIII alone and FVIII and emicizumab during the study follow-up will be examined in the SoC Cohort as a sensitivity analysis. If treatment switching between SoC classes is observed in >30% of the SoC Cohort, participant characteristics and the primary outcome will be compared between participants who switched SoC treatment versus not to see if there are significant differences between these two SoC sub-Cohorts (standardized mean difference (SMD) > 0.25 or clinically significant after reviewed by clinical experts). If significant differences of outcome between these two SoC sub-Cohorts is detected, separate comparisons will be conducted between Roctavian Cohort and two SoC sub-Cohorts for all outcomes.

As noted in Section 7.3.3, participants in the SoC Cohort who are administered Roctavian after study consent will be removed from the analytic dataset.

Table 4: HA Treatments*

Treatment Type	Treatment Class	Treatment Name	Recommended Treatment Frequency and/or Dose
SoC	Emicizumab	Emicizumab (Hemlibra)	3 mg/kg once every week for the first 4 weeks; Then, 1.5 mg/kg once every week, 3 mg/kg every 2 weeks, or 6 mg/kg every 4 weeks
	SHL products	Kovaltry (Octocog alfa)	20-40 IU/kg administered 2-3 times weekly
		Lonoctocog alfa (Afstyla)	20-50 IU/kg administered 2-3 times weekly
		Octocog alfa (Advate)	20-40 IU/kg every 2-3 days
		Moroctocog alfa (ReFacto)	20-40 IU/kg at intervals of 2-3 days
		Simoctocog alfa (Nuwiq)	20-40 IU/kg at intervals of 2-3 days
		Turoctocog alfa (NovoEight)	20-40 IU/kg administered every second day or 20-50 IU/kg administered 3 times weekly

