	EHL products	Damoctocog alfa pegol (Jivi)	45-60 IU/kg every 5 days; Based on clinical characteristics, dose can also be 60 IU/kg every 7 days or 30-40 IU/kg 2 times per week; Maximum dose per injection for prophylaxis should not be higher than approximately 6000 IU

Treatment Type	Treatment Class	Treatment Name	Recommended Treatment Frequency and/or Dose
		Efmoroctocog alfa (Elocta)	50 IU/kg every 3-5 days; Dose may be adjusted to 25-65 IU/kg based on response
		Rurioctocog alfa pegol (Adynovi)	40-50 IU/kg twice weekly in 3-4-day intervals
		Turoctocog alfa pegol (Esperoct)	50 IU/kg every 4 days
	PD products	Voncento	20-40 IU/kg at intervals of 2-3 days
		Beriate	20-40 IU/kg at intervals of 2-3 days
		Octanate	20-40 IU/kg at intervals of 2-3 days
		Haemoctin	20-40 IU/kg at intervals of 2-3 days
		Faktor VIII SDH – Intersero	20-40 IU/kg at intervals of 2-3 days
		Haemate P	One IU of FVIII activity per kg body weight increases the circulating FVIII level by approximately 2.0 IU/dL. Individualize dosage based on weight, type and severity of hemorrhage, FVIII level, and presence of inhibitors.
Roctavian	N/A	Valoctocogene roxaparvovec (Roctavian)	6×10^{13} vg/kg body weight, administered as a single intravenous infusion

Abbreviations: EHL: extended half-life; IU: international units; kg: kilogram; mg: milligram; N/A: not applicable; PD: plasma-derived; SHL: standard half-life; SoC: standard of care; vg: vector genomes

*Note: During the analysis phase, the final list of SoC treatments are expected to be confirmed based on the participants enrolled in the study and their observed data; the final list will be updated for the final study report as necessary.

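### SAP Table 5 defines the last treatment for a bleed without limiting it to bleed treatment, so routine FVIII doses can merge consecutive same-site bleeds and lower the SoC bleeding rate

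*Protocol*

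**What the plan says.** The counting rule for the primary endpoint stands in SAP section 7.4.3, Table 5, row Treated ABR. Protocol section 7.2.5.1 refers to protocol section 10.3 and the SAP for how bleeds on consecutive days are counted. Section 10.3 gives no merging rule, so Table 5 holds the only one.

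Three parts of that row matter:

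- A bleed counts as treated under a condition tied to the reason for treatment: "If bleed date is within 3 calendar days of treatment date where occasion for treatment is one of the hemorrhage values", or where the therapy scheme is on demand.
- The merging rule opens with "Two bleeds of the same localization are considered to be one bleed if the second occurs within 3 calendar days from the date of", and the date meant is that of the final treatment given for the earlier bleed.
- It then fixes the term: "The last treatment is defined as the last treatment before a new bleed occurs, either in the same or in a different location". No occasion or therapy scheme is named here.

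SAP section 7.4.2, Table 4 lists SHL and PD regimens such as "20-40 IU/kg every 2-3 days" and "20-40 IU/kg at intervals of 2-3 days", and an EHL regimen of "50 IU/kg every 4 days". Other EHL intervals run up to 7 days, and emicizumab is given every 1, 2 or 4 weeks. Protocol section 3.2.2.2 says "it is necessary to inject plasma-derived or standard half-life FVIII concentrates at least 3 times per week".

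**The concern.** The two halves of the merging rule disagree. The lead clause speaks of treatment for the first bleed. The definition accepts whatever treatment came last before the next bleed at any site. The row above filters by occasion; the definition does not.

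For a man on FVIII every 2-3 days, the last dose before any bleed is almost always within 3 days of it. Under the definition, his next bleed at the same site is then absorbed into the previous one even if months separate them. A man off prophylaxis after Roctavian has no such dose, so his bleeds are counted separately.

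The miscount would therefore differ between cohorts in the primary endpoint. It would carry into major and joint ABR, which are built on the treated-bleed definition. Two programmers could each follow the text and count differently, and independent double-programming cannot say which of them is right.

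**Working it through.** **Plan's own figure.** SAP section 7.6 gives SoC rate 3, Roctavian rate 0.85, dispersion 1.5, exposure 1 year, allocation 0.2, margin 0.5, one-sided 2.5% and 80% power.

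- V1 = 1/3 + 1/(0.2 × 0.85) + 1.2 × 1.5/0.2 = 15.216
- V0 = (1 + 0.5 × 0.2)² / (0.5 × 0.2 × (3 + 0.2 × 0.85)) + 9 = 12.817
- log 0.5 − log(0.85/3) = 0.568
- N1 = (1.960 × √12.817 + 0.8416 × √15.216)² / 0.568² = 328.8

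This gives 329 and 66, against the stated 330 and 67. Power at 330/67 is 80.6%.

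**One record under the definition.** A man on FVIII every second day has left-ankle bleeds on 1 March and 1 September and none between. His last dose before 1 September is 1 or 2 days earlier, so the rule counts one bleed. The same man off prophylaxis was last treated in March, so the rule counts two. Now add a right-knee bleed on 1 June. The search for the March bleed's last treatment stops there, on 30 or 31 May. The September bleed is then about 93 days later and is counted. Only same-site bleeds with nothing elsewhere in between can merge.

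**Size.** The documents give no figure for the rule's effect, so it was simulated. Bleeds were gamma-Poisson (3 per year, dispersion 1.5), each treated on its day, with FVIII at a fixed interval over 1 year. A bleed merges if it falls 3 days or less after the last dose of any kind given before the first new bleed at any site. The site distributions are assumptions; the documents give none. Roctavian participants without prophylaxis stay at 0.83-0.85. The ratio is that value over the SoC rate at 2-day dosing. Power uses the formula above with dispersion held at 1.5, so it is approximate.

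| Sites | SoC ABR, every 2 days | Every 4 days | Bleed treatment only | Ratio (2 days) | Power at 330/67 |
|---|---|---|---|---|---|
| 8 equal | 2.70 | 2.77 | 2.97 | 0.314 | 64% |
| 6 equal | 2.60 | 2.70 | 2.96 | 0.326 | 57% |
| 0.6/0.2/0.1/0.1 | 2.00 | 2.24 | 2.91 | 0.421 | 13% |
| 2 equal | 1.81 | 2.09 | 2.90 | 0.465 | 6% |

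At the extreme of a single site, the counted rate is about 0.7 and the ratio exceeds 1. Over 3 years with 2-day dosing, the four rows give 2.64, 2.53, 1.83 and 1.61. With 8 sites that is a loss of 1 − 2.64/3 = 12%.

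The ratio and power columns suppose that the whole SoC Cohort is on such FVIII. If 70% were (an assumption) and the rest unaffected, the SoC rate would be 0.7 × 2.60 + 0.3 × 3 = 2.72 for 6 sites, 2.30 for the concentrated case and 2.17 for 2 sites. The ratios would be about 0.31, 0.37 and 0.39.

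**Longer intervals.** At 7 days the counted rate is 2.81 (6 sites), 2.54 (concentrated) and 2.43 (2 sites); at 14 days it is 2.88, 2.72 and 2.66. EHL regimens above 3 days are thus partly affected, and emicizumab least.

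**Bleed treatment only.** The counted rate is 2.80 (1 site) to 2.97 (8 sites) of 3.0, a loss of 1-7%. That is the ordinary merging of bleeds that really are close together.

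**The case against.** The harmless reading is a natural one. The lead clause says that the treatment is for the first bleed, and the definition can be taken as saying only where that series of treatments ends. The neighbouring bullets deal with bleed treatment, and occasion and therapy scheme are listed fields for this variable. Read so, almost nothing is lost. This stands as evidence of intent, and it means that the undercount is not certain. It does not remove an explicit definition that says something wider.

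The data may also not hold dated routine doses. The Treated ABR row lists therapy start and end, and infusion numbers are derived from usage periods and frequency. Yet the row for prophylactic treatments in Table 5 lists a treatment date. Whether the wider reading can be programmed dose by dose is open.

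Four stronger inferences are tempting and not supported:

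- A reader might infer that every later bleed at a site collapses into the first, so that the SoC rate roughly halves even with many sites. The definition ends the search at a new bleed in any location, which keeps the loss near 12% for 8 equal sites over 3 years. Larger losses need bleeds concentrated in few sites.
- A reader might infer that the proportions with zero bleeds change. Merging never removes a participant's first bleed, so whole-period zero-bleed counts are identical with and without it.
- A reader might infer that the rule favours the product. A lower SoC rate raises the ratio, which works against Roctavian.
- A reader might infer that only the SoC Cohort is touched. Roctavian participants still on FVIII after infusion, or back on it, are affected in the same way under the treatment policy estimand.

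**Conclusion.** The point holds as a defect of definition in the only counting rule for the primary endpoint. As defined, the rule lets a prophylactic dose stand as the last treatment for a bleed. It then merges consecutive same-site bleeds in men dosed every 2-3 days, whatever the gap.

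Depending on how bleeds spread over sites, a true SoC rate of 3 would be counted as about 1.8 to 2.7 in one year. If all SoC participants were so dosed, the ratio would move from 0.283 to between about 0.31 and 0.47, with a clear loss of power against the 0.5 margin. A mixed cohort shifts less. These sizes rest on assumed site distributions and on the wider reading; under the narrower reading the loss is 1-7%. The bias runs against Roctavian, but it distorts the estimate and should be removed before the first data cut.

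**What to change.** In SAP Table 5, replace the definition with one sentence: the last treatment is the last administration recorded with a bleeding occasion (or on-demand scheme) for that same bleed, meaning the same localization and bleed date. State that prophylactic, surgical and other-occasion doses do not count when bleeds are merged. The major and joint rows inherit the change because they refer back to treated bleeds.

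The cost is that sentence and the matching program line. Occasion is already a DHR field for this variable, so no new data are needed.
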